7. STUDY COHORT AND SAMPLE-SIZE JUSTIFICATION

The enrollment target is 4,650 subjects per treatment arm, for a total of 9,300 subjects. The assumed treatment effect size of high-dose vs. standard-dose influenza vaccine is derived from our meta-analysis of randomized trials of relatively healthy outpatients comparing these two active vaccination treatments, with an estimated risk reduction of 27% for the composite endpoint. After conservatively diluting the treatment effect among those with active heart disease by 35%, treatment with high-dose influenza vaccine is expected to result in an 18% risk reduction, i.e., a hazard ratio of 0.82, in all-cause death or cardiovascular hospitalizations, with an anticipated similar magnitude for all-cause death and cardiopulmonary hospitalizations. Based on data from contemporary clinical trials of patients with coronary heart disease or heart failure [1-9] the event rate for the primary endpoint is estimated to be 9% during the subject's 1st enrolling season following randomization for each subject, reducing to 8% during each subject's 2nd enrolling season, and 7% during each subject's 3rd enrolling season after vaccination, with 30% of the primary composite endpoint being death and 70% being cardiopulmonary hospitalization. Considering a follow-up to the end of summer phone call on July 31 (before the next influenza season) and a conservative 30% rate of not being vaccinated in each subsequent influenza season, a trial of 9,300 subjects with 500 subjects for the Vanguard year in 2016-2017 and 2,933 new subjects in each of the three influenza seasons in 2017-2018, 2018-2019 and 2019-2020 is projected to result in 45, 291, 440 and 519 primary endpoint events by the end of the 2016-2020 enrolling seasons for a total of 1,296 events. Assuming two interim analyses for efficacy using the O'Brien-Fleming group sequential method at the end of 2017-2018 and 2018-2019 influenza seasons, the trial will have power of 0.943 to detect an 18% risk reduction or power of 0.913 to detect a 17% risk reduction at a two-sided significance level of 0.05.

If proportion not vaccinated in each subsequent season is 20%, the trial will have power of 0.954 and 0.929 to detect a risk reduction of 18% and 17%, respectively. On the other hand, if proportion not vaccinated in each subsequent season is 40%, the trial will have power of 0.929 and 0.896 to detect a risk reduction of 18% and 17%, respectively.

8. STATISTICAL METHODS

8.1 General Principles

All statistical data analyses will be performed using SAS (SAS Institute, Inc., Cary NC) and R (R Foundation for Statistical Computing, Vienna, Austria. <http://www.R-project.org>).

Analyses of efficacy and safety endpoints will employ the mITT analysis as described in Section 5, except for the analysis of baseline data and the secondary efficacy endpoints in 4.2.1, total (first recurrent) cardiopulmonary hospitalizations or all-cause death across all enrolling seasons, and in 4.2.3, time to first occurrence of all-cause death or cardiopulmonary hospitalization, both across all enrolling reason, which will employ the ITT analysis.

With the mITT analysis to efficacy and safety analysis, each subject will potentially contribute endpoints more than once over multiple influenza seasons, and endpoints in each subject may be correlated. In order to account for the intra-subject correlation over multiple influenza seasons, a robust variance estimator will be used in statistical inference. Due to the randomization-once strategy, those returning for re-vaccination following the initial vaccination after randomization constitute non-random cohorts. This may introduce bias due to potential differential survivorship and drop-out after the initial randomization.

8.2 Analysis of Baseline Data

We will assess the balance in the randomization groups with regard to subject's baseline data including cardiovascular disease measures in all randomized subjects, i.e. the ITT population. The subjects will be compared on each characteristic between the randomized vaccine arms using methodology appropriate for the measure. In addition, baseline subject and disease characteristics at randomization will be summarized using descriptive statistics such as mean and standard deviation or median and interquartile range (IQR) for quantitative measurements and frequency and proportion for binary or categorical measurements and using graphical summaries with box plots or empirical distribution functions for quantitative measurements and bar plots for binary or categorical measurements.

8.3 Analysis of the Primary Efficacy Endpoint

8.3.1. Primary efficacy analysis

The primary efficacy analysis will be performed on the primary endpoint of the time to first occurrence of all-cause death or cardiopulmonary hospitalization within each enrolling season according to the mITT analysis described above in Section 6. All randomized unique patients who received vaccinations at the beginning of enrolling seasons are included. If a patient does not return for re-vaccination for a subsequent season as per the randomization-once strategy, that patient is not included for that or any subsequent enrolling seasons. Each patient can contribute events in multiple consecutive seasons in which they are vaccinated. The event accrual period will begin 2 weeks following receipt

of influenza vaccine and continue until summer phone call (July 31st) follow-up with the time to first event as elapsed time from vaccination.

The primary efficacy analysis will be based on a two-sided log-rank test with robust variance at a significance level of 0.05, stratified by enrolling season. The Kaplan-Meier method will be used to estimate the survival distribution for the time to first event for the composite of all-cause death or cardiopulmonary hospitalization. An unadjusted estimate of the hazard ratio and confidence interval will be obtained using a Cox proportional hazards model with only treatment as a model term, stratified by enrolling season (Cox, 1972) with robust variance estimation (Wei, Lin and Weissfeld, 1989).

8.3.2 Secondary efficacy analysis

A secondary analysis of the primary efficacy endpoint will be based on a Cox proportional hazards model with robust variance estimation (Wei, Lin and Weissfeld, 1989) with treatment (high-dose trivalent or standard-dose quadrivalent influenza vaccination), age group (< 65 or ≥ 65 years old), baseline cardiovascular (CV) risk group (AMI or HF), past vaccination history/pattern (to adjust for the theoretical possibility of interference between successive vaccinations, both prior to randomization and after randomization), match between vaccine and circulating influenza strains, and the interaction between treatment and match for circulating B (Yamagata)-lineage that is included only in the standard-dose QIV (binary), based on influenza typing and subtyping data from Canada and the US to account for the differences in B vaccine antigens present only in the standard-dose QIV as model terms, stratified by enrolling season, to obtain an adjusted hazard ratio for treatment with confidence intervals.

It is thought that the study population is at risk for the primary efficacy endpoint of all-cause death or cardiopulmonary hospitalization secondary to complications of influenza. Therefore a secondary “in season” analysis will be undertaken, limited to an evaluation of efficacy during influenza season with start and end of season defined according to the Centers for Disease Control and Prevention (CDC) and Public Health Agency of Canada surveillance system. We will use information provided in the CDC’s Flu View Report which is updated on a weekly basis (<http://www.cdc.gov/flu/weekly/>). For each state, we will use the point at which influenza transitions from “sporadic” to “local” on the graphic “Geographic Spread of Influenza as Assessed by State and Territorial Epidemiologists”, and as a sensitivity analysis we will use the point of transition from “minimal” to “low” activity on the “ILINet State Activity Indicator Map”. A similar approach will be utilized for each province in Canada.

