## 9.0 STUDY PROCEDURES

### 9.1 Screening/Baseline Visit

- Obtain written informed consent and medical release of information form
- Review medical records for past medical history (including recent hospitalization and previous influenza vaccinations) and current medications (will be also be assessed annually if enrolled)
- Reconfirm eligibility (if baseline visit is on a later date than the screening visit)
- Collect medical history, social history, baseline questionnaires (i.e frailty survey; NYHA/CCS functional status), demographics and contact information for follow-up, including the patient's social security number (US only) or provincial health insurance number (for Canada only)- when permissible according to local ethics regulations, the names and contact information of two family members or friends that could be contacted if the subject is unreachable
  - For participants with documented evidence of adult congenital heart disease (ACHD) participating in the correlative ACHD substudy, additional medical and surgical history will be collected.
- Review medical records for height, weight, and temperature (if available)
- Patients must not be given study vaccination prior to Randomization
- Blood will be drawn for baseline measurement of antibody titers and other biomarkers in a subset of consenting subjects
- Randomize subject via the internet using the Statistical Registration and Randomization System
  - The StaRRS randomization software will return a treatment code corresponding to either high-dose or standard-dose vaccine
  - Labels containing the treatment allocation code will be on the drug packet. Verify correct assignment.
- Dispense and administer vaccine (all efforts should be made to vaccinate same day as randomization)
- Monitor subject for at least 20 minutes post vaccination for injection site and allergic reactions
- Dispense 7 day AE diary with instructions for reporting recorded information at the one week follow up phone call
- Provide a proof of vaccination letter to those who may require it
- Schedule one-week follow-up contact

#### 9.1.2 PATIENTS RETURNING FOR YEAR 2 AND 3

- Review medical records for past medical history (including recent hospitalization and previous influenza vaccinations) and current medications
- Confirm that the patient does not meet exclusion criteria

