8.8 Subgroup Analysis

Many baseline characteristics are known to be prognostic or suspected to be confounders for the clinical outcomes in the study population with high-risk cardiovascular disease. They include age, sex, race/ethnicity, smoking status, obesity (BMI \geq 30), baseline CV risk group (AMI vs HF), diabetes, renal dysfunction, and use of statin and beta-blocker medications. Influenza season is also known to affect the clinical outcome. Internal consistency of the primary analysis will be assessed in subgroups defined by these and other baseline characteristics. Heterogeneity of efficacy will be assessed using interaction

tests of treatment by each of these baseline covariates and by influenza season. Any interaction test resulting in a heterogeneity p-value < 0.10 will be further evaluated for clinical plausibility of effect modification.

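### The secondary adjusted Cox model in SAP 8.3.2 uses only age cut at 65 and AMI/HF as prognostic baseline terms, so its hazard ratio is slightly attenuated and makes little use of measured risk

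*SAP*

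**What the plan says.** The primary analysis in SAP 8.3.1 has no baseline covariates. It is a "two-sided log-rank test with robust variance at a significance level of 0.05, stratified by enrolling season", and the hazard ratio comes from a "Cox proportional hazards model with only treatment as a model term, stratified by enrolling season".

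Adjustment appears in SAP 8.3.2, which opens: "A secondary analysis of the primary efficacy endpoint will be based on a Cox proportional hazards model with robust variance estimation". The prognostic baseline terms listed there are "age group (< 65 or ≥ 65 years old), baseline cardiovascular (CV) risk group (AMI or HF"). The list then passes straight to vaccine terms: "baseline cardiovascular (CV) risk group (AMI or HF), past vaccination history/pattern". The remaining terms are that vaccination history, before and after randomization (entered for possible interference between successive vaccinations), match between vaccine and circulating strains, and a treatment-by-match interaction for the B-Yamagata lineage.

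SAP 8.8 says: "Many baseline characteristics are known to be prognostic or suspected to be confounders for the clinical outcomes". It names ten: age, sex, race/ethnicity, smoking, obesity, AMI/HF, diabetes, renal dysfunction, statin use and beta-blocker use. They are used there for subgroups and interaction tests. Protocol 9.1 also collects "baseline questionnaires (i.e frailty survey; NYHA/CCS functional status"), and no SAP model names either item.

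On subjects who come back in later seasons, SAP 8.1 says that "those returning for re-vaccination following the initial vaccination after randomization constitute non-random cohorts".

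**The concern.** A reader who wants a treatment effect adjusted for patient risk will go to SAP 8.3.2, the only outcome model the SAP prespecifies for that purpose. It carries two of the ten factors in SAP 8.8, one of them dichotomised, and neither functional class nor frailty.

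Two things follow. First, in a Cox model, leaving out predictors of outcome pulls the treatment hazard ratio toward 1, even under perfect randomization. Second, randomization protects the comparison at first vaccination but does not guarantee balance among subjects who survive and return. Measured risk factors bear on the interpretation of those later seasons, and the adjusted model uses almost none of them.

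**Working it through.** **Count of terms.** Of the ten SAP 8.8 factors, age and AMI/HF are in SAP 8.3.2. The other eight are not.

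**Plan's own event projection (SAP 7).** Inputs: 500 new subjects, then 2,933 in each of three seasons; event rates 9%, 8% and 7% in a subject's first, second and third season; 30% of events are deaths; 30% not revaccinated each later season. With deaths removed, the fraction carried forward is 1 − 0.3 × 0.09 = 0.973 after a first season and 1 − 0.3 × 0.08 = 0.976 after a second.

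- 2016-2017: 500 × 0.09 = 45.0
- 2017-2018: 2,933 × 0.09 + 500 × 0.973 × 0.7 × 0.08 = 264.0 + 27.2 = 291.2
- 2018-2019: 264.0 + 2,933 × 0.973 × 0.7 × 0.08 + 500 × 0.973 × 0.7 × 0.976 × 0.7 × 0.07 = 264.0 + 159.8 + 16.3 = 440.1
- 2019-2020: 264.0 + 159.8 + 2,933 × 0.973 × 0.7 × 0.976 × 0.7 × 0.07 = 264.0 + 159.8 + 95.5 = 519.3

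The total is 1,295.6, against 1,296 stated.

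**Share from returning subjects.** First-season events are 9,300 × 0.09 = 837. The rest, 1,296 − 837 = 459, are 459 / 1,296 = 35%.

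**Plan's own power.** For 1:1 allocation, the expected Z is √(1,296 / 4) × |ln 0.82| = 18 × 0.1985 = 3.572. Against the final boundary of 1.98, power is Φ(3.572 − 1.98) = 0.944. A three-look calculation with boundaries 4.25, 2.67 and 1.98 gives 0.945 (stated 0.943). At HR 0.83 it gives 0.917 (stated 0.913). These figures are for the unadjusted primary comparison; the SAP states none for the adjusted model.

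**Gain from fuller adjustment.** The documents give no prognostic strength, so this part rests on assumptions. The simulation used 15,900 subject-seasons, an 8.15% event rate (about 1,300 events), conditional HR 0.82, exponential times, a normal prognostic index with 30% of its variance already carried by age group and AMI/HF, and 400 runs per setting. Gain in effective events = (Z with full index / Z with current terms)², from unrounded Z.

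| Prognostic SD | HR, current terms | HR, full index | SE of log HR (both) | Z, current | Z, full | Gain in effective events | Power at 1,296 events, HR 0.82 |
|---|---|---|---|---|---|---|---|
| 0.5 | 0.819 | 0.817 | 0.0558 | 3.579 | 3.617 | 2.2% | 0.945 to about 0.949 |
| 0.8 | 0.822 | 0.819 | 0.0558 | 3.505 | 3.582 | 4.5% | 0.945 to about 0.953 |
| 1.0 | 0.825 | 0.819 | 0.0558 | 3.445 | 3.580 | 8.0% | 0.945 to about 0.959 |

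In events, 2.2% of 1,296 is about 29 and 8.0% is about 104. The standard error does not move. The whole gain is the conditional hazard ratio lying further from 1.

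**Sensitivity.** An SD of 1.3 gives 17% and about 2.5 power points. If the current terms carry 20% of the variance instead of 30%, the ratio of mean Z at SD 1.0 is 1.054, or 1.054² − 1 = 11%. Both simulations treat the fuller model as capturing all of the prognostic variance, which is a best case.

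**The case against.** The strongest reply is that nothing powered is affected. A reader might infer that fuller adjustment would lift the stated 0.943 and 0.913. It would not: those belong to the unadjusted log-rank test in SAP 8.3.1, which should stay as it is, and no power is claimed for SAP 8.3.2. This stands, so the power points above are only a scale for the size of the effect. They are not the power of the 8.3.2 treatment coefficient either. The simulated models have no season strata, repeat subjects, robust variance, vaccination history or match terms. With 0/1 coding of the interaction, that coefficient is the hazard ratio in unmatched strata alone. If half the events fell there (assumption), fixed-design power would be Φ(√(648 / 4) × 0.1985 − 1.96) = 0.71.

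A reader might also infer that adjustment would narrow the confidence interval. The constant standard error shows otherwise.

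The two terms do have a source. Protocol 13.18.2 prespecifies post-stratification by age at 65, AMI/HF and season. That explains the choice, but it does not show that two factors are enough.

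Nor is the bias from returning subjects left unaddressed, as one might conclude from SAP 8.1 alone. SAP 8.4 weights them by the inverse probability of remaining on study. Those weights model retention, not outcome, and patient-level covariates are named only for the third-season weights, in general terms. Outcome adjustment complements that analysis; it is not the sole safeguard.

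Two limits on the covariate list also stand. SAP 8.8 calls its factors prognostic or suspected confounders, so it does not declare all ten prognostic, and it names neither NYHA/CCS nor frailty. And it would be wrong to assume that every eligibility item is held for everyone: inclusion criterion 4 in Protocol 7.0 needs only one risk factor, and Protocol 9.1 does not list LVEF as a baseline measurement.

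**Conclusion.** The point holds as a low-cost improvement to a secondary analysis. The SAP 8.3.2 model adjusts for only two coarse prognostic factors while others are listed in SAP 8.8 or collected under Protocol 9.1. Its hazard ratio is slightly attenuated (at SD 1.0, about 0.825 against 0.819), and it makes little use of measured risk among the subjects who supply 35% of projected events.

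The size is modest: about 2-8% in effective events for an assumed prognostic SD of 0.5 to 1.0, with 30% of that variance already captured and the fuller model capturing the rest. Only much stronger covariates would move it past two power points at 1,296 events. Adjustment can address measured imbalance among returning subjects, not unmeasured differences. The primary test, its error rate and its stated power are untouched.

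**What to change.** In SAP 8.3.2, keep AMI/HF, vaccination history and the match terms. Replace age group with continuous age, and add values recorded at randomization for sex, diabetes, renal dysfunction, smoking, BMI, NYHA/CCS class and frailty score. Include LVEF or prior-hospitalization items only if they are confirmed as recorded for all subjects. State that missing baseline covariates are handled by simple imputation, so that no subject drops out of the model. Leave SAP 8.3.1 and the power statement in SAP 7 unchanged.

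The cost is SAP wording, a longer model and a small amount of imputation; for example, Protocol 9.1 takes height and weight from medical records only where available. The adjusted figure will also be a conditional hazard ratio that differs slightly from the unadjusted one, and the report should say so.

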8.3.3 Exploratory efficacy analysis

An exploratory analysis of the primary efficacy endpoint is to compare the two vaccination group according to the effectiveness of vaccine relative to virulence of influenza strain and the quality of match between influenza strain and vaccine within each influenza season

(see Section 2.4.1). This analysis will be based on Cox proportional hazards regression model with treatment, the effectiveness of vaccine relative to virulence of influenza strain, and the quality of match between influenza strain and vaccine within each influenza season as model terms, stratified by enrolling season.

8.4 Sensitivity Analysis

In order to account for potential differential survivorship bias and bias due to differential drop-out after the initial randomization with the randomization-once strategy, we will use a propensity score method based on the inverse probability of treatment weighting (IPTW) approach by Xie and Liu (2005) for adjusted Kaplan-Meier estimator, log-rank test and Cox proportional hazards regression analysis using inverse probability of treatment weighting for non-random cohorts, stratified by enrolling season. Specifically, observations from re-vaccinated subjects from previous seasons will be inversely weighted by the probabilities of their remaining on study by the start of the enrolling season. Such probabilities will be estimated by a product of the patient-level survival function estimators for the composite of death and dropout (including failure to re-vaccinate at beginning of the enrolling season) for each of the prior seasons. Weights for the treatment in the third enrolling season will be estimated to adjust for patient-level covariates such as demographics and disease characteristics in addition to treatment assignment in a Cox model. In order to account for the randomness in the estimate of the inverse probability of treatment weighting and for the intra-subject correlation over multiple vaccinations, robust variance will be estimated using bootstrap method as suggested by Austin (2016).

8.5 Analysis of the Secondary Efficacy Endpoints

Analysis of the secondary efficacy endpoints will be grouped into two, one based on the mITT analysis of the secondary efficacy endpoints given in 4.2.2 and 4.2.4 and the other based on the ITT analysis of the secondary efficacy endpoints given in 4.2.1 and 4.2.3

8.5.1 mITT Analysis

Analysis of the secondary efficacy endpoint in 4.2.2, time to first occurrence of cardiovascular death or cardiovascular hospitalization subject to competing risk of death other than cardiovascular death within each enrolling season will be performed using standard method for competing risk (Gray, 1988; Fine and Gray, 1999) with a sandwich-type robust variance estimate, ignoring the presence of non-random cohorts of those who returned for revaccination following the first vaccination according to the randomization-once strategy.

Analysis of the secondary efficacy endpoint in 4.2.4, time to first occurrence of the individual components of the primary endpoint, i.e. all-cause death and cardiopulmonary hospitalization, within each enrolling season will be based on the standard methods for time to event data for all-cause death and on the standard

method for competing risk for cardiopulmonary hospitalization subject to competing risk of all-cause death.

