To maximize accuracy of outcome ascertainment compared with details obtained through clinical follow up, subject medical records and administrative health insurance claims data will be periodically reviewed during, at the end, and after the trial period to document vital status, potential cause of death, and hospitalizations. Where permissible, the CCC and DCC will link trial data in accordance with privacy-protected and data-secure health insurance claims data agencies (in Canadian sites only) in order to minimize loss to follow-up and provide enhanced detection of safety and outcomes as recommended by guidance documents from Canadian regulatory health authorities.

For all subjects, when vital status cannot be ascertained study personnel may search public death records for confirmation and cause of death.

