4.2. Secondary Efficacy Endpoints

- 4.2.1. Total (first and recurrent) cardiopulmonary hospitalizations or all-cause death across all enrolling seasons
- 4.2.2. Time to first occurrence of cardiovascular death or cardiovascular hospitalization within each enrolling season
- 4.2.3. Time to first occurrence of all-cause death or cardiopulmonary hospitalization across all enrolling seasons
- 4.2.4. Time to first occurrence of individual components of the primary efficacy endpoint, i.e. cardiopulmonary hospitalization and all-cause death, within each enrolling season

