6. DEFINITIONS

With most efficacy endpoints being time to event data, specification of censoring is critically important. Censoring rule will be specific to whether the endpoints are analyzed based on mITT analysis or ITT analysis.

An endpoint event is defined as all-cause death or cardiopulmonary hospitalization.

For mITT analysis: All randomized unique patients who received vaccinations at the beginning of enrolling seasons are included. If a patient does not return for re-vaccination for a subsequent season as per the randomization-once strategy, that patient is not included for that or any subsequent enrolling seasons. Each patient can contribute events in multiple consecutive seasons in which they are vaccinated. Events are included in the analysis if they occurred after 2 weeks post vaccination but before July 31 of the enrolling season. Any event occurring within 2 weeks after vaccination will not count as an event. If a patient dies within 2 weeks after vaccination, time to event will be censored on the date of death. If a patient experiences a non-fatal event within 2 weeks after vaccination, that event will not count as an event. If a patient has not experienced any endpoint event before July 31 of each enrolling season, time to event is censored at the last date known to be alive before July 31 of each enrolling season. If the last date known to be alive is on or after July 31 of the enrolling season, time to event is censored as of July 31. Time to event for each enrolling season is the elapsed time from vaccination and is determined as $\text{event/censoring date} - \text{vaccination date} + 1$.

For ITT analysis: All randomized unique patients are included, regardless of whether they were vaccinated on study or not, and followed through July 31, 2019, the date of data-cutoff. If a

patient has not experienced any endpoint event before July 31, 2019, time to event is censored at the last date known to be alive before July 31, 2019. If the last date known to be alive is on or after July 31, 2019, time to event is censored as of July 31, 2019. Time to event is an elapsed time from randomization and is determined as event/censoring date – randomization date + 1.

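### All-cause death as a separate endpoint is analysed only within season in vaccinated subjects; a supplementary analysis from randomization in all randomized subjects should be added

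*SAP*

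**What the plan says.** SAP 4.2.4 defines the endpoint as "Time to first occurrence of individual components of the primary efficacy endpoint, i.e. cardiopulmonary hospitalization and all-cause death, within each enrolling season". SAP 8.5 splits the secondary endpoints into two groups and places this one in the mITT group, "one based on the mITT analysis of the secondary efficacy endpoints given in 4.2.2 and 4.2.4"; the ITT group holds only 4.2.1 and 4.2.3. The season limit is then repeated in SAP 8.5.1: "time to first occurrence of the individual components of the primary endpoint, i.e. all-cause death and cardiopulmonary hospitalization, within each enrolling season". SAP 8.1 sets the same default: "Analyses of efficacy and safety endpoints will employ the mITT analysis as described in Section 5, except for the analysis of baseline data", with 4.2.1 and 4.2.3 as the other exceptions.

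SAP 6 gives the mITT rules. Only vaccinated subject-seasons enter. A subject who misses a revaccination is out of that season and all later ones. Events count from two weeks after vaccination to July 31. For early deaths: "If a patient dies within 2 weeks after vaccination, time to event will be censored on the date of death".

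The ITT set in SAP 6 takes every randomized subject, vaccinated or not, with time from randomization and a July 31, 2019 cut-off. It serves two efficacy endpoints, both composites: total cardiopulmonary hospitalizations or death (4.2.1) and first death or cardiopulmonary hospitalization across seasons (4.2.3).

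The Protocol leads to the same place. Section 10.2.4 puts no season limit on the components, but 13.5 analyses them like the primary endpoint and 13.17 makes mITT the primary sample for all outcomes.

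**The concern.** Death happens once, and it also decides who can return. A subject who dies between July 31 and the next vaccination leaves no event in the within-season analysis and is simply absent from the next season. SAP 8.1 concedes that "those returning for re-vaccination following the initial vaccination after randomization constitute non-random cohorts" and that differential survivorship and drop-out may bias the result.

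The planned response is the inverse-probability weighting in SAP 8.4. That section names no endpoint, but SAP 1.3 introduces it for the primary efficacy endpoints. For 4.2.4, SAP 8.5.1 offers only standard time-to-event and competing-risk methods.

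The two ITT composites do not fill the gap. Endpoint 4.2.3 stops at the first event, and 70% of first events are planned to be hospitalizations, so a death after one of these is not seen. Endpoint 4.2.1 pools deaths with hospitalizations, and in the added mean-frequency analysis death is the terminal event, not the outcome compared. The trial would therefore report a mortality hazard ratio drawn partly from acknowledged non-random cohorts, with no from-randomization estimate beside it.

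**Working it through.** **Inputs (SAP 7).** New subjects: 500, then 2,933 in each of three seasons. Primary event rates: 9%, 8% and 7% in a subject's first, second and third season. Deaths are 30% of first events. Non-revaccination is 30% per later season. Hazard ratio (HR) 0.82, 1:1 allocation, two-sided 0.05.

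**Step 1: reproduce the plan's events.** Returners in the next season = current subjects × (1 − 0.30 × event rate) × 0.70, for at most three seasons.

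| Season | First season | Second | Third | Events |
|---|---|---|---|---|
| 2016-17 | 500 | – | – | 45.0 |
| 2017-18 | 2,933 | 340.6 | – | 291.2 |
| 2018-19 | 2,933 | 1,997.7 | 232.7 | 440.1 |
| 2019-20 | 2,933 | 1,997.7 | 1,364.8 | 519.3 |

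The total is 1,295.6, against 1,296 stated.

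**Step 2: share of subject-seasons in returners.**
- To July 31, 2019: (340.6 + 1,997.7 + 232.7) / 8,937 = 2,571 / 8,937 = 29%.
- Through 2019-20: 5,933 / 15,232 = 39%.

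**Step 3: first-event deaths in mITT.**
- To July 31, 2019: 0.30 × (45.0 + 291.2 + 440.1) = 233.
- Through 2019-20: 0.30 × 1,296 = 389.

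**Step 4: deaths from randomization in all randomized.** Seasonal death rates are 0.30 × 9/8/7% = 2.7%, 2.4% and 2.1%. I assume that they hold in non-returners too, with 2.1% in a fourth season, and that vital status is known.
- To July 31, 2019: Vanguard 13.5 + 11.7 + 10.0; 2017-18 cohort 79.2 + 68.5; 2018-19 cohort 79.2. Sum about 262, over 10,181 person-seasons.
- Through 2019-20: add 9.8 + 58.5 + 68.5 + 79.2. Sum about 478, over 19,218 person-seasons.

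**Step 5: deaths outside the planned mortality analysis.**
- To July 31, 2019: 262 − 233 = 29. With 20% and 40% non-return, mITT deaths are 0.30 × 808.0 = 242 and 0.30 × 745.2 = 224, so the range is 20 to 38.
- Through 2019-20: 478 − 389 = 89 (64 to 113 over the same range).

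These differences reflect non-return only, plus a fourth Vanguard season in the later figure. They add nothing for the summer gap or the first 14 days. Deaths within 14 days of vaccination, at constant hazard over an assumed counting window of 28 to 44 weeks, would be 389 × 2/44 to 389 × 2/28 = 18 to 28 through 2019-20, and 233 × 2/44 to 233 × 2/28 = 11 to 17 to July 31, 2019.

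**Step 6: power for death at HR 0.82.** Power = Φ(0.1985 × √(D/4) − 1.96), where 0.1985 = |ln 0.82| and D is the number of deaths.
- D = 233: 0.33. D = 262: 0.36.
- D = 389: 0.50. D = 478: 0.58.
- 80% power needs 798 deaths.

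These counts take only deaths that are the first primary event. If deaths after a hospitalization raised the total 1.25 to 2 times (an assumption), ITT through 2019-20 would hold 597 to 956 deaths, with power 0.68 to 0.87.

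**The case against.** The strongest reply is that the added analysis would not be cleanly protected by randomization. Subjects who decline revaccination are taken off study and no longer followed (Protocol 8.12 and 9.2, SAP 5.1), and endpoints are collected only to July 31 of the season (Protocol 11.3 and 11.4.2). The back-up sources are permissive: "For all subjects, when vital status cannot be ascertained study personnel may search public death records for confirmation and cause of death". Claims linkage under Protocol 9.2 is limited to Canadian sites where permitted, and the US linkage in Appendix C needs consent. Many non-returners could be censored when they leave, so self-selection would enter through censoring. This stands. It limits what the analysis can show, but 4.2.3 already carries the same limit, and the analysis would still start from the randomized groups and include early deaths and never-vaccinated subjects.

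The seasonal clock also has a stated reason: Protocol 13.18.1 holds that later events in people not revaccinated are unlikely to relate to the earlier vaccination. Analysing a component in the same set and window as its composite is conventional, so 4.2.4 is not itself an error. That stands too.

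A reader might go further than the documents allow in three ways:
- That death is never handled by ITT. It is, inside 4.2.1 and 4.2.3.
- That the mortality hazard ratio rests only on survivors who return. First seasons supply 6,366 of 8,937 planned subject-seasons (71%) to July 31, 2019, and 9,299 of 15,232 (61%) through 2019-20.
- That the data for a full ITT mortality analysis are already in hand. The follow-up rules above say otherwise for subjects who leave.

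**Conclusion.** The concern holds in a limited form. The plan gives all-cause death a separate comparison only under mITT within season, with no bias check for that endpoint and no from-randomization counterpart.

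At the SAP's ITT cut-off, about 29 of some 262 projected deaths fall outside the planned mortality analysis; through 2019-20 it is about 89 of 478. Both figures rest on the sponsor's event rates and 30% non-return, equal death rates in non-returners, and complete vital status. With incomplete vital status the recoverable number is smaller; known summer and early deaths would add to it.

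Neither the direction nor the size of any bias in the mortality hazard ratio can be derived from the documents, and none is claimed. Death is one component of one secondary endpoint, and the primary conclusion does not depend on it. The addition is still worth making, because it is cheap and rests on a better-defined comparison.

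**What to change.** In SAP 8.5.2, add as a supplementary analysis, reported beside the within-season result:
- Time from randomization to all-cause death in all randomized subjects: Kaplan-Meier, log-rank and Cox, stratified by randomization year, with the same cut-off as 4.2.3.
- Deaths within 14 days of vaccination and any known deaths between seasons are counted.
- Subjects who leave are censored at the date last known alive, unless the record, claims or death-record searches in Protocol 9.2 supply vital status. Report by arm how many were resolved each way.
- Any statement on mortality refers to this analysis.

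Reconcile the July 31, 2019 ITT cut-off in SAP 6 with the final analysis after 2019-2020 in SAP 8.10, since the expected death count depends on it.

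The cost is one table and one figure, plus whatever searches are made. Two limits remain: deaths after a subject leaves will be only partly ascertained, so drop-out can still bias the result, and power for death alone is modest, about 0.58 at HR 0.82 at best through 2019-20 on the first-event counts.
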